# **DNA** samples

The use of DNA to search for biomarkers of disease and drug action is exploratory. Any results from this DNA study will not be placed in the subject's medical records.

To maximize confidentiality, all samples and the information associated with the samples will be double-coded to prevent the exposure of the subject's information and identity. This double-coding process allows Novartis to go back and destroy the sample at the subject's request. In addition, sample information is stored in one secured database while genetic data is stored in an independent secured database.

#### 8.5.3.1 Sputum biomarkers

The examination of QBW251 effect on inflammatory markers, which may include but are not limited to IL-6 and IL-8 will be done in sputum.

16S rRNA PCR may be performed to measure the bacterial load. If feasible, the analysis will be performed using remaining sputum samples collected for microbiology assessment.

Sputum samples will be biobanked for potential exploratory sputum bacterial profile measured by 16s rRNA gene sequencing.

Both 16S rRNA PCR and 16s rRNA gene sequencing are optional to China.

#### 8.5.3.2 Serum protein levels

Protein profiling applying highly multiplexed exploratory analytical platform and hypothesis free data analysis (SomaScan) may be applied to identify biomarker signatures, related to disease and/or QBW251 mode of action. Given the exploratory nature of the work, the analytical method used for this assessment is not validated and the results from this exploratory analysis will not be included in the clinical study report. This assessment is optional to China.

# 8.5.3.3 Use of residual biological samples

Any residual samples remaining after the protocol-defined analysis has been performed may be used for additional exploratory analysis related to the purpose of this study. This may include but is not limited to using residual samples for protein binding, metabolite profiling, biomarkers of transporters or other bioanalytical purposes (e.g., cross check between different sites and/or stability assessment). Residual PK plasma samples remaining after the determination of QBW251 may be used for exploratory assessment of metabolites or other bioanalytical purposes (e.g., cross check between different sites, stability assessment).

Given the exploratory nature of the work, the analytical method used for those assessments will not be validated. As such, the results from this exploratory analysis will not be included in the clinical study report.

# 9 Study discontinuation and completion

#### 9.1 Discontinuation

#### 9.1.1 Discontinuation of study treatment

Discontinuation of study treatment for a subject occurs when study treatment is stopped earlier than the protocol planned duration and can be initiated by either the subject or the investigator.

Subjects may voluntarily discontinue study treatment for any reason at any time.

The investigator must discontinue study treatment for a given subject if he/she believes that continuation would negatively impact the subject's well-being.

Study treatment must be discontinued under the following circumstances:

- Subject/guardian decision
- Pregnancy: a positive urine pregnancy test after start study drug requires immediate interruption of study drug until serum hCG is performed and found to be negative. If positive, the subject must discontinue study medication.
- Use of prohibited treatment outlined in Section 6.2.2.
- Any situation in which study participation might result in a safety risk to the subject.
- Following emergency unblinding
- Emergence of an AE reported as severe and suspected to be related to investigational drug or an SAE reported and suspected to be related to the investigational drug.

- Any laboratory abnormalities that in the judgment of the investigator, taking into consideration the subject's overall status, prevents the subject from continuing participation in the study.
- Any liver event requiring immediate discontinuation of study treatment, as specified in Table 16-2
- Individual serum creatinine increase ≥ 50% compared to baseline (must be confirmed).
   Please refer to Section 16.3 for discontinuation criteria due to emerging renal abnormalities.
- Study drug can be temporarily interrupted as a response to the occurrence of adverse events that do not fulfill the requirements above described for permanent discontinuation (refer to Section 6.5.1).

Discontinuation of study treatment will be at the discretion of the Investigator under the following circumstances:

- Any other protocol deviation that results in a significant risk to the subject's safety.
- Emergence of adverse event(s) or laboratory abnormalities that in the judgement of the Investigator, taking into account the subjects' overall status, prevent the subject from continuing participation in the study.

The appropriate personnel from the site and Novartis will assess whether study treatment should be discontinued for any subject whose treatment code has been broken inadvertently. Unblinding for emergency reasons requires study drug discontinuation.

If a female subject of childbearing potential withdraws from the study prematurely, the investigator should recommend her to maintain contraceptive measures for at least 7 days after the last dose of the study drug.

If discontinuation of study treatment occurs, the investigator should make a reasonable effort to understand the primary reason for the subject's premature discontinuation of study treatment and record this information.

Subjects who discontinue study treatment or who decide they do not wish to participate in the study further should NOT be considered withdrawn from the study UNLESS they withdraw their consent (see Section 9.1.2 'Withdrawal of Informed Consent'). Where possible, they should return for the assessments indicated for EOS (V1999) in the Assessment Schedule (Table 8-1). If they fail to return for these assessments for unknown reasons, every effort (e.g. telephone, e-mail, letter) should be made to contact the subject/pre-designated contact as specified in the lost to follow-up section (Section 9.1.3). This contact should preferably be done according to the study visit schedule.

If the subject cannot or is unwilling to attend any visit(s), the site staff should maintain regular telephone contact with the subject, or with a person pre-designated by the subject. This telephone contact should preferably be done according to the study visit schedule.

After study treatment discontinuation, at a minimum, in abbreviated visits, the following data should be collected at clinic visits or via telephone/email contact:

- New / concomitant treatments
- Adverse Events / Serious Adverse Events

The investigator must also contact the IRT to register the subject's discontinuation from study treatment.

If discontinuation occurs because treatment code has been broken, please refer to Emergency breaking of treatment code Section 6.6.3.

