### 8 Visit schedule and assessments

Assessment schedule (Table 8-1) lists all of the assessments when they are performed. All data obtained from these assessments must be supported in the subject's source documentation.

Subjects should be seen for all visits/assessments as outlined in the assessment schedule (Table 8-1) or as close to the designated day/time as possible. Missed or rescheduled visits should not lead to automatic discontinuation. Subjects who prematurely discontinue the study for any reason should be scheduled for a visit as soon as possible, at which time all of the assessments listed for the final visit will be performed. At this final visit, all dispensed investigational product should be reconciled, and the adverse event and concomitant medications recorded on the CRF.

Table 8-1 Assessment Schedule

EPOCH	Scree	ning	Treatment										End o	f Study	Unscheduled									
Visit Name	Screening	Baseline 		Treatment												End of Study		Unscheduled						
Visit Numbers 	1	20				100				110 				120				13	30	14	10	1999		150
Days	-42 to -1	1 -3 +1		1							28 ±3							56 ±3		84 ±3		91 ±3	114 ±3	-
Weeks				1						2				4				8		12		13	17	-
Time (post-dose)	-	-	0h4	1h	2h	3h	4h	6h	8h	-	0h 	1h	2h	3h	4h	6h	8h	0h 	3h	0h 	3h	-	-	-
Informed consent	Χ																							
Inclusion / Exclusion criteria	Х	Х																						
Demography	Χ																							
Medical history/current medical conditions	Х																							
Bronchiectasis exacerbation history	Х																		·					
Smoking history	Х																							

EPOCH	Scree	ening									Tre	atm	ent									End o	f Study	Unscheduled
Visit Name	Screening	Baseline 		Treatment											End of Study	Safety Follow Up	Unscheduled							
Visit Numbers 	1	20			1	00				110 				120				1:	30	14	10	1999		150
Days	-42 to -1	1 -3 +1				1				14				28 ±3					6 3	8 ±		91 ±3	114 ±3	-
Weeks						1				2				4					3	1	2	13	17	-
Time (post-dose)	-	-	0h4	1h	2h 3	h	4h	6h	8h	-	0h 	1h	2h	3h	4h	6h	8h	0h4	3h	0h4	3h	-	-	-
Randomization			Χ																					
Study drug administration 										b	.i.d. o	dosir	ng											
In-clinic study drug administration			Х								Х							Х		X				
Rescue medication dispensation 	S																							
Drug accountability													S											
Concomitant medications										>	(													

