Physical Examination 	S	S									S							S		S		S		S
Body Height	Χ																							
Body Weight	Χ																					Χ		
Body Temperature	Χ	Х	Χ								Х							Χ		Χ		Х		X
Blood Pressure	Х	Х	Χ								Х							Χ		Χ		Х		Χ
Pulse rate	Χ	Х	Χ								Х							Χ		Χ		Χ		Χ
Clinical Chemistry 	Х		Χ								Х							Χ		Χ				Χ
Coagulation 	Χ		Χ								Х							Χ		Χ				X
Hematology	Х		Χ								Х							Χ		Χ				Χ
Urinalysis	Х		Χ								Х							Χ		Χ				Χ
Pregnancy and assessments of fertility 	Х		Х								Х							Х		Х		Х		Х

EPOCH	Scree	ning	Treatment														End o	f Study	Unscheduled					
Visit Name	Screening	Baseline 													End of Study	Safety Follow Up	Unscheduled							
Visit Numbers 	1	20	100							110 	120							130 140			40	1999		150
Days	-42 to -1	1 -3 +1		1						14	28 ±3								6 3	84 ±3		91 ±3	114 ±3	•
Weeks			1				2	4						8			12 1		17	-				
Time (post-dose)	-	-	0h4	1h	2h	3h	4h	6h	8h	-	0h 	1h	2h	3h	4h	6h	8h	0h4	3h	0h 	3h	-	-	-
Electrocardiogram (ECG) 	Х		Х			X					Х			Х				X	Х	Х	Х	Х		Х
St. George's Respiratory Questionnaire (SGRQ)		Х																		х				
EQ-5D-3L		Х																		Х				
Quality of Life Questionnaire for Bronchiectasis (QOL-B)		х									х							X		x				
eDiary										Х														X
EXACT-PRO 	X 											Χ												X
HRCT 	X 																			X 				
Spirometry	Х		Χ								Х							Χ		Х				X
Spirometry reversibility test	Х																							
Oxygen Saturation	Χ																							
Sputum bacterial load 	Χ	Х									Х							Χ		Х				X
Sputum 16S rRNA PCR		Х									Х							Χ		Х				
Exploratory Biomarkers in Sputum		Х									х							Х		Х				
Exploratory sputum bacterial profile		Х																		х				

EPOCH	Scree	ening									Tre	atm	ent									End of Study		Unscheduled
Visit Name				Treatment													End of Study	Safety						
Visit Numbers 	1	20		100						110 	120							1:	30	140		1999		150
Days	-42 to -1	1 -3 +1		1					14	28 ±3							56 ±3		84 ±3		91 ±3	114 ±3	-	
Weeks						1				2	4			8		12		13	17	-				
Time (post-dose)	-	-	0h 	1h	2h	3h	4h	6h	8h	-	0h4	1h	2h	3h	4h	6h	8h	0h4	3h	0h 	3h	-	-	-
Exploratory Biomarkers in Blood		Х									Х									Х				

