#### 8.5.2 Pharmacokinetics

PK samples will be collected as per visits and time points indicated in the Assessment Schedule (Table 8-1). Instructions outlined in the laboratory manual regarding sample collection, numbering, processing and shipment shall be followed.

PK sampling (pre-dose and 3 hour post-dose) will be conducted and evaluated in all subjects on Days 1, 28, 56 and 84 (end of treatment).

Additionally, although serial PK sampling is optional, efforts will be made to have approximately 30-40 patients from selected sites undergo serial PK sampling up to 8 hours post-dose at Day 1 and Day 28 visits as per Table 8-1 to further characterize the PK profile of QBW251 in BE patients, which will provide important understanding of the 300 mg b.i.d. dose in BE patients.

Furthermore, in case a patient prematurely discontinued treatment but continue participation in the study, the first visit after the discontinuation should have a PK trough assessment and thereafter subsequent PK sampling should be suspended.

Plasma PK samples will be evaluated only in subjects who have been administered QBW251. QBW251 concentration will be determined by a validated LC-MS/MS method with an anticipated lower limit of quantification (LLOQ) of 1 ng/mL of QBW251.

Concentrations below the LLOQ will be reported as zero and missing data will be labeled as such in the bioanalytical report.

The following pharmacokinetic parameters will be determined using the actual recorded sampling times and non-compartmental method(s) with Phoenix WinNonlin (Version 8 or higher): Cmax, Tmax, AUClast, AUC0-12h, T1/2,eff when feasible.

Residual plasma samples remaining after the determination of QBW251 may be used for exploratory assessment of metabolites or other bioanalytical purposes (e.g. cross check between different sites, stability assessment).

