# 9.1.5 Early study termination by the sponsor

The study can be terminated by Novartis at any time for any reason. This may include reasons related to the benefit/risk assessment of participating in the study, practical reasons (including slow enrollment), or for regulatory or medical reasons. In taking the decision to terminate, Novartis will always consider the subject welfare and safety. Should early termination be necessary, subjects must be seen as soon as possible and treated as a prematurely withdrawn subject and undergo all assessments of the premature withdrawal visit. The Investigator should ensure contact is made as quickly as possible by telephone and/or e-mail and/or letter. If the study is stopped for a change in the benefit/risk assessment or for medical reasons, patients may be instructed to stop taking the investigational drug QBW251 immediately. Else, patients may be instructed to continue QBW251 intake until they can return to the site for a final assessment. The investigator may be informed of additional procedures to be followed in order to ensure that adequate consideration is given to the protection of the subject's interests. The investigator or sponsor depending on the local regulation will be responsible for informing IRBs/IECs of the early termination of the trial.

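### Early stoppers are sent to an EOS visit that schedules no laboratory panels, sputum, spirometry, QOL-B or PK, and the visit named for sponsor termination is not defined

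*Protocol*

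**What the plan says.** Four places in the protocol describe what happens when a patient stops early, and each describes it differently.

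- **Section 9.1.1**, on stopping study treatment: where possible, "they should return for the assessments indicated for EOS (V1999) in the Assessment Schedule". It then sets a floor for later contacts: "After study treatment discontinuation, at a minimum, in abbreviated visits, the following data should be collected at clinic visits or via telephone/email contact". The listed data are concomitant treatments and adverse events.
- **Section 8**, on prematurely discontinuing the study: a visit as soon as possible, "at which time all of the assessments listed for the final visit will be performed". No visit number is given.
- **Section 9.1.5**, on termination by the sponsor: patients are to be "treated as a prematurely withdrawn subject and undergo all assessments of the premature withdrawal visit". If the reason is neither benefit/risk nor medical, "patients may be instructed to continue QBW251 intake until they can return to the site for a final assessment".
- **Section 8.5.2**, for patients who stop treatment but stay in the study: "the first visit after the discontinuation should have a PK trough assessment".

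Section 3.1 places the end-of-treatment safety, lung function and PRO assessments at Day 84, not at EOS. Three rules decide which data count:

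- Section 12.4.3 limits the primary CFU analysis to one day after the last dose.
- Section 12.5.2 and SAP 7.2 run the safety on-treatment period to one week after the last dose.
- Section 12.1 and SAP 4 admit a patient to the PD analysis set only with a baseline and at least one post-baseline assessment.

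**The concern.** The only visit that 9.1.1 names for an early stopper is one at which the trial's laboratory panels and visit-based efficacy measures are not scheduled. Sites following different sections could also collect different data from similar patients.

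The larger stake is safety. The stopping reasons in 9.1.1 include severe suspected adverse events, laboratory abnormalities, liver events and a confirmed creatinine rise. Patients with tolerability problems are therefore likely to be among the stoppers, and their laboratory values near the last dose carry much of the information. Section 4.2 reports a trend to GGT elevation at higher plasma levels that small numbers made hard to interpret, and 10.2.3 has since stood down the Data Monitoring Committee.

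The second stake is the visit-based secondary endpoints: fibrinogen, FEV1/FVC, QOL-B and bacterial clearance. Rescue-medication use is recorded daily in the eDiary and is not affected in the same way.

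**Working it through.** **1. Read Table 8-1 by column.** Rows that do carry an EOS mark (weight, vital signs, ECG, pregnancy test) confirm the column position.

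| Assessment | Scheduled visits | EOS (V1999) | Unscheduled |
|---|---|---|---|
| "Sputum bacterial load" | Screening, Baseline, Days 28, 56, 84 | no | yes |
| Spirometry | Screening, Days 1, 28, 56, 84 | no | yes |
| QOL-B | Baseline, Days 28, 56, 84 | no | no |
| Chemistry (with hsCRP), coagulation (with fibrinogen), haematology, urinalysis | Screening, Days 1, 28, 56, 84 | no | yes |
| Sparse PK | Days 1, 28, 56, 84 | no | no |
| ECG, pregnancy test | Screening, Days 1, 28, 56, 84 | yes | yes |
| Temperature, blood pressure, pulse | Screening, Baseline, Days 1, 28, 56, 84 | yes | yes |
| Weight | Screening | yes | no |

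The table has no premature withdrawal column. The PK trough requested in 8.5.2 has no matching entry at EOS. Section 4.5.1 plans blood collection at the end of the study, but the EOS column has no routine blood panel, only a serum or urine pregnancy test.

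**2. Dosing time left without a scheduled panel (visit windows ignored).** Day 1 samples are pre-dose and Day 14 is a telephone call.

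- Stop before Day 28: the last panel is the Day 1 pre-dose one, so up to 28 − 1 = 27 days of dosing are uncovered. There is no scheduled post-baseline sputum, spirometry or QOL-B, and for those measures the patient drops out of the PD set.
- Stop between Days 28 and 56: up to 56 − 28 = 28 days.
- Stop between Days 56 and 84: up to 84 − 56 = 28 days.

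A panel taken within 7 days of the last dose would fall inside the safety on-treatment period. Section 12.5.2 also plans shift tables against the worst on-treatment value, which a missing last panel could understate.

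**3. How many patients.** Inputs are from Protocol 12.8.1.

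- The plan's N: 60 / (1 − 0.16) = 71.4, rounded up to 72. This reproduces.
- The plan's power: SE = 2.8 × √(2/30) = 0.723; 1.5 / 0.723 = 2.075; 2.075 − 1.282 = 0.793; power = Φ(0.793) = 0.786, stated as 79%. It reproduces with a one-sided 10% level. A two-sided 10% level gives 0.666.
- Planned drop-outs: 72 × 0.16 = 11.5, or 72 − 60 = 12.

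The point changes no sample-size figure. Power at 36 per arm would be 0.839, but that would need every drop-out to supply a true week-12 value, which an early-stop visit cannot do.

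**4. Which samples would count.**

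- Safety laboratory: up to one week after the last dose.
- Primary CFU model: up to one day after the last dose.
- Fibrinogen and FEV1/FVC: sections 12.5.1.2 and 12.5.1.4 state no such limit, and SAP 6.2 keeps these endpoints as descriptive summaries.

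**The case against.** The strongest reply is that limiting sampling after the stop is a defensible choice. The study is non-confirmatory, and the primary estimand is a hypothetical on-treatment effect at week 12 with no imputation. Sputum taken more than one day after the last dose would be excluded. Day 28 and Day 56 values already collected on treatment stay in the repeated-measures model. The supplementary estimands in 12.4.4 concern antibiotics, not treatment discontinuation, and SAP 6.1.4 cancels them. Tests can also reach the database through unscheduled visits, repeat testing of laboratory adverse events (8.4.1) or liver and renal follow-up. All of this stands, and it removes most of the case for the primary endpoint. It does not supply a routine laboratory panel or secondary measurement at stopping.

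Three stronger readings are tempting, and the documents do not support them.

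- **That patients are sent to EOS at sponsor termination.** Section 9.1.5 does not say so. It names a visit that is undefined; EOS is only the nearest candidate.
- **That on-drug samples were lost when this study ended.** The SAP records termination but gives neither the reason nor the number then on drug. Continued dosing until the final assessment is conditional on the reason, and even then 9.1.5 only permits it.
- **That 8.5.2 contradicts 9.1.1.** Section 9.1.1 does not restrict early stoppers to the EOS visit; it also speaks of abbreviated and clinic visits. What remains is that EOS has no PK entry.

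**Conclusion.** The point holds as a gap in scheduled assessments and as an inconsistency between sections 8, 8.5.2, 9.1.1, 9.1.5 and Table 8-1. Followed as written, an early stopper has no routine laboratory panel, sputum, spirometry or QOL-B at stopping, and one who stops before Day 28 has none after the first dose. EOS does provide ECG, vital signs and a pregnancy test.

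The size is at most about 11 to 12 of 72 patients under the planned 16% drop-out. That is a ceiling: patients who withdraw consent or are lost to follow-up would not attend the visit, and some stops fall close to a scheduled visit. Patients still on treatment at termination would add to the number, but the documents do not give that count.

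The loss falls mainly on safety laboratory and secondary data. For the primary analysis the gain is confined to sputum taken on drug or within one day of the last dose, which 9.1.5 permits at termination but does not ensure.

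**What to change.** In sections 8, 9.1.1 and 9.1.5 and in Table 8-1, define one early-discontinuation/termination visit under one name, held as close as possible to the last dose. Assign it the Day 84 (V140) assessments except HRCT: at minimum the four laboratory panels, sputum, spirometry and QOL-B. Reconcile it with the PK trough in 8.5.2. The Day 84 column also holds an in-clinic dose and 3-hour post-dose time points, so the text must say that the set means the assessments and how the post-dose ones are treated in a patient already off drug.

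Flag sputum by the existing one-day rule and safety data by the existing one-week rule. State in the SAP to which nominal visit, if any, an early-stop value is assigned. If no patient remains in the study, report by arm how many early stoppers had a laboratory panel and a sputum sample inside those windows.

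The cost is amendment wording and one extra set of already-defined assessments per early stopper, with some samples off-treatment and of limited use. No dosing or stopping rule changes.

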#### 9.1.2 Withdrawal of informed consent

Subjects may voluntarily withdraw consent to participate in the study for any reason at any time. Withdrawal of consent occurs only when a subject:

- Does not want to participate in the study anymore, and
- Does not allow further collection of personal data

In this situation, the investigator should make a reasonable effort (e.g. telephone, e-mail, letter) to understand the primary reason for the subject's decision to withdraw his/her consent and record this information.

Study treatment must be discontinued and no further assessments conducted, and the data that would have been collected at subsequent visits will be considered missing.

Further attempts to contact the subject are not allowed unless safety findings require communicating or follow-up.

All efforts should be made to complete the assessments prior to study withdrawal. A final evaluation at the time of the subject's study withdrawal should be made as detailed in the assessment table (Table 8-1).

Novartis will continue to keep and use collected study information (including any data resulting from the analysis of a subject's samples until the time of withdrawal) according to applicable law.

For EU and RoW: All biological samples not yet analyzed at the time of withdrawal will no longer be used, unless permitted by applicable law. They will be stored according to applicable legal requirements.

